Sustained Cure	All pretherapy signs and symptoms ^b of the index infection(s) have resolved (or returned to "preinfection status") with no evidence of resurgence AND no additional antibiotic therapy (beyond IV study therapy) was required, AND , for cIAI subjects, no unplanned surgical procedures or percutaneous drainage procedures have been performed.
Cure	All pretherapy signs and symptoms ^b of the index infection(s) have resolved (or returned to "preinfection status") AND no additional IV antibiotic therapy is required, AND , for cIAI subjects, no unplanned surgical procedures or percutaneous drainage procedures have been performed.
Failure	No apparent or insufficient response to IV study therapy in prestudy signs and symptoms of the index infection(s): persistence, progression, or improvement (without full resolution) of all pretherapy signs and symptoms ^c
Relapse	Subjects with a favorable clinical response (cure or improved) at the EOT visit have worsening signs and symptoms ^b of the index infection(s) by the EFU or Day 28 post-therapy visit.
Indeterminate	Study data are not available for evaluation of efficacy for any reasons, including: a) Complication related to underlying medical condition; OR b) Subject was withdrawn for any reason before sufficient data had been obtained to permit evaluation of clinical response; OR c) Extenuating circumstances preclude classification as "sustained cure," "failure," or "relapse;" OR d) Death occurred during the study period and the index infection was clearly noncontributory.
^a A favorable clinical response at EFU or Day 28 post-randomization requires an assessment of "cure" or "sustained cure". To be considered "sustained cure", the clinical response for the prior visit must have been considered "cure". A clinical response of "cure" is only relevant at EFU for subjects with a response of "improved" at EOT. ^b Refer to Table 13 for a description of disease-specific clinical signs and symptoms.	

4.2.3.1.1.3 Microbiological Response

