Superinfection	An infection-site culture grows a uropathogen (at $\geq 10^5$ CFU/mL) other than a baseline pathogen during the course of IV study therapy OR emergence during IV study therapy of a new pathogen at a distant (non-urine), sterile site along with worsening signs and symptoms of infection.
Indeterminate	a) Follow-up urine culture is not available at the EOT visit ^c due to subject death or withdrawal from study; OR b) Microbiological data are incomplete; OR c) Assessment not possible due to protocol violation; OR d) Any other circumstance which makes it impossible to define the microbiological response
^a A microbiological response rating will be determined separately for each qualifying pathogen isolated at baseline. ^b If a new/emergent pathogen is identified after initiation of IV therapy which was not identified at baseline, regardless of susceptibility profile, the microbiological response rating for the new pathogen will be considered “superinfection”. ^c A favorable overall microbiological response at EOT requires “eradication” or “sustained eradication” of all baseline pathogens. ^d A microbiological response of “sustained eradication” at EOT is used when the microbiological response assessment at OTX visit was also “eradication”. ^e A microbiological response of “eradication” at EOT is used when this is the first time that microbiological response assessment is “eradication (i.e., OTX visit microbiological response assessment was not “eradication”). ^f If a subject is discontinued from IV study therapy due to clinical failure (i.e., unfavorable clinical response), but persistence of the admission pathogen is not confirmed by culture results or no culture is obtained at the time of clinical failure, the admission pathogen will be presumed to have persisted. ^g If a culture is not available at EOT, an assessment at this visit can be made from the last available urine culture which was collected after at least 48 hours of IV study therapy.	

Table 8 Definitions of the By-Pathogen Microbiological Response at the EFU Visit

Microbiological Response ^{a,b,c}	Response Definition
Sustained eradication ^d	A urine culture taken at the EFU visit still shows eradication of the uropathogen (e.g., $\geq 10^5$ CFU/mL is reduced to $< 10^4$ CFU/mL) found at study entry.
Persistence	A urine culture taken at the EFU visit grows a uropathogen (at $\geq 10^4$ CFU/mL) found at study entry.

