New Infection	A uropathogen, other than a microorganism found at baseline is present in the urine (at a level $\geq 10^5$ CFU/mL) any time after IV study therapy is finished; OR A pathogen is isolated from a distant (non-urine), sterile after IV study therapy has been completed.
Recurrence	A urine grows a uropathogen (at a level $\geq 10^5$ CFU/mL) taken any time after documented eradication.
Indeterminate	a) Follow-up urine culture is not available at the EFU visit due to subject death or withdrawal from study; OR b) Microbiological data are incomplete; OR c) Assessment not possible due to protocol violation; OR d) Any other circumstance which makes it impossible to define the microbiological response
^a A microbiological response rating will be determined separately for each qualifying pathogen isolated at baseline. ^b If a new/emergent pathogen is identified after EOT which was not identified at baseline, regardless of susceptibility profile, the microbiological response rating for the new pathogen will be considered “new infection”. ^c A favorable overall microbiological response at EFU visit requires “sustained eradication” of all baseline pathogens. ^d A microbiological response of “sustained eradication” at EFU is used when the microbiological response assessment at EOT visit is also “eradication”.	

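### The favourable labels in Table 5 (footnote a) and Table 8 depend on the previous visit's label, so some subjects who are well at the endpoint visit have no favourable category

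*Combined protocol and SAP*

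**What the plan says.** **Clinical response (Section 4.2.3.1.1.1.2, Table 5).** Only *cure* and *sustained cure* are favourable at EFU and Day 28. Footnote a adds two conditions based on history. For *sustained cure*, "the clinical response for the prior visit must have been considered" *cure*. And *cure* "is only relevant at EFU for subjects with a response of" *improved* at EOT. The rows for these two labels describe the subject's state and do not refer to the label at the previous visit. The *failure* row covers "persistence, progression, or improvement (without full resolution) of all pretherapy signs and symptoms", and *relapse* needs worsening.

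**Microbiological response (Tables 7 and 8).** *Sustained eradication* "at EOT is used when the microbiological response assessment at OTX visit was also" *eradication* (Table 7, footnote d). In Table 8 the only favourable EFU label is *sustained eradication*, which "at EFU is used when the microbiological response assessment at EOT visit is also" *eradication* (footnote d). Table 8 has no plain *eradication* row. Table 7, footnote g, lets a missing EOT culture be replaced by the last one taken after at least 48 hours of therapy.

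**Use of the labels.** Table 2 makes Day 28 clinical response the primary component for cIAI, with both *cure* and *sustained cure* favourable. It makes EFU clinical plus microbiological response the component for cUTI, and survival the component for HABP/VABP. Day 28 clinical response in all strata is a key secondary endpoint (Section 3.2.1). Section 4.2.3.1.1.1.2 refers to Section 8.2 for further detail on the favourable/unfavourable split. Section 8.2.5.1 contains only a missing-visit rule (rate as indeterminate, with exceptions for lack of efficacy), and Table 16 sets missing to failure. Section 8.0 says there will be no separate SAP.

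**The concern.** A favourable outcome should follow from the subject's condition at the endpoint visit, unless the plan deliberately says otherwise. Here the footnotes make it depend on a chain of earlier labels, and the chain has breaks. A subject who falls into a break is resolved, so *failure* and *relapse* do not fit. Only *indeterminate* is left, and Table 2 does not count that as favourable. The result would be a non-response in the primary endpoint for someone observed to be well. With 5 to 10 subjects per arm and stratum, a few such cases change the reported rates visibly. If they fall unevenly between arms, they also shift the between-group estimate.

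**Working it through.** **1. Clinical label paths.** Take a subject who is fully resolved at EFU and at Day 28, with separate EFU and Day 28 visits and no further antibiotic or procedure. Consider three readings of footnote a:

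- A (literal): *sustained cure* needs *cure* at the prior visit; *cure* exists only at EFU after *improved*.
- B: the limit on *cure* applies at EFU only; *cure* is free at Day 28.
- C: as A, but *sustained cure* at the prior visit also satisfies the condition.

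| EOT | EFU label (A, B, C) | Day 28, A | Day 28, B | Day 28, C |
|---|---|---|---|---|
| improved | cure | sustained cure | sustained cure | sustained cure |
| cure | sustained cure | none | cure | sustained cure |
| cure or improved, EFU unrated | not rated | none | cure | none |
| indeterminate | none | none | cure | none |

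The second row is the subject who responds early and stays well. The gap there arises under A only, and A conflicts with Table 2, which lists *cure* as favourable for cIAI at Day 28. The last row has no favourable EFU label under any of the three readings, and EFU is the cUTI visit. For cUTI, *cure* at EOT followed by *sustained cure* at EFU is favourable even literally.

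**2. Microbiology.** If the EOT rating is indeterminate and the EFU culture is clear, *sustained eradication* is not available and Table 8 offers no other favourable row. Footnote g of Table 7 helps only when the EOT culture is missing and an earlier on-therapy culture qualifies. The clinical rating has no equivalent.

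**3. Size per subject.** Section 8.2.7 gives 10 (Group 1) and 5 (Group 2) per infection type, and 30 and 15 overall.

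- Stratum rate: 1/10 = 10 points; 1/5 = 20 points.
- Pooled rate: 1/30 = 3.3 points; 1/15 = 6.7 points.

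**4. Range under the literal reading only.** First, the plan's own figure. The Agresti & Coull interval is p̃ ± 1.96·√[p̃(1−p̃)/ñ], with ñ = n + 1.96² and p̃ = (x + 1.96²/2)/ñ. For 24/30, ñ = 33.84, p̃ = 25.92/33.84 = 0.766, and the interval is (62.3, 90.9), as in Table 18. Of the 16 rows, 15 reproduce. The upper limit for 4/10 computes to 68.8 against 66.8 printed, which has no bearing here.

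Now assume a true response of 80% in each arm and stratum, so cIAI responders are 8 of 10 and 4 of 5. Let s be the share of them already *cure* at EOT. The documents do not give s, so the whole range is shown. The favourable counts are 24 − 8s of 30 and 12 − 4s of 15.

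| s | Group 1 (95% CI) | Group 2 (95% CI) |
|---|---|---|
| 0 | 24/30 = 80.0% (62.3, 90.9) | 12/15 = 80.0% (54.0, 93.7) |
| 0.5 | 20/30 = 66.7% (48.7, 80.9) | 10/15 = 66.7% (41.5, 85.0) |
| 1 | 16/30 = 53.3% (36.1, 69.8) | 8/15 = 53.3% (30.1, 75.2) |

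If early cure differs by arm, say 6 of 8 against 1 of 4, the rates are 18/30 = 60.0% and 11/15 = 73.3%. A true difference of zero (90% CI −19.3, 23.6) then becomes −13.3 points (−35.1, 12.3). These are unstratified Miettinen and Nurminen intervals; the plan stratifies where appropriate, so they are illustrative.

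**The case against.** The best reply is that nobody would apply footnote a literally. Table 2 and the footnote's own first sentence name *cure* as favourable at Day 28, and the rows describe such a subject well. On that view the footnote only separates two labels that are both favourable. This has force for the early, lasting responder: readings B and C both rescue that subject. It does not dispose of the point. Clinical ratings are made by investigators at many sites, Section 8.2 gives no ruling, and the eCRF instructions are not in the documents. Whether sites would in fact differ is unknown.

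The reply does not reach the indeterminate EOT. A rater could give a favourable label there only by setting the footnote aside. Other rules should keep such cases down: EOT falls within 24 hours of the last dose, and subjects who stop therapy are still followed (Section 7.1.4.1). That limits the number but does not supply a label.

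Two stronger inferences are tempting and should not be drawn.

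- A reader might infer that cUTI subjects who clear by Day 3, and so are *sustained eradication* at EOT, can never be favourable at EFU. The wording is loose, but that reading is strained. The Table 8 row asks whether the culture still shows eradication, and footnote d says the EOT rating is also *eradication*. Table 7 gives both EOT labels the same colony-count criterion and counts both as favourable, and the Sponsor assigns the rating. The documents give no Day 3 clearance rate either.
- A reader might infer that any clear EFU culture should count, whatever happened at EOT. Treating documented persistence at EOT as unfavourable is a defensible choice. Section 8.2.5.1 also presumes persistence at all later time points after discontinuation for lack of efficacy, and an unconditional rule would contradict it.

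**Conclusion.** The point stands, and the footnotes should be corrected before unblinding.

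- Footnote a of Table 5, taken literally, contradicts Table 2 and the table's own rows for subjects cured at EOT who stay well to Day 28. This bears on the cIAI primary component and on the key secondary Day 28 clinical response in every stratum. It depends on the literal reading and on separate EFU and Day 28 visits.
- An indeterminate EOT followed by full resolution, or by a clear culture, at EFU has no favourable label under any reading considered. This bears on the cUTI primary component.
- The HABP/VABP primary component is unaffected.

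Each affected subject costs 10 or 20 points of a stratum rate and 3.3 or 6.7 points of the pooled rate, at the planned mMITT sizes. How many will be affected cannot be derived from the documents. The fall from 80.0% to as low as 53.3% in the working illustrates the literal reading under an assumed 80% response; it is not a forecast.

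**What to change.** **Table 5, footnote a.** Let *sustained cure* accept either *cure* or *sustained cure* at the prior visit. Let a subject who meets the *cure* row at EFU or Day 28 be rated *cure*, and so favourable, when the prior visit was indeterminate or missing. Except subjects who are already failures for lack of efficacy under Section 8.2.5.1.

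**Table 8, footnote d.** Accept *eradication* or *sustained eradication* at EOT. Count a clear EFU culture as favourable when the EOT rating was indeterminate. Keep the presumption of persistence in Section 8.2.5.1, and say outright that documented EOT persistence remains unfavourable. Footnote c of Table 8 and the cUTI line of Table 2 need matching words.

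**Cost.** A short amendment to the footnotes and Table 2, with matching eCRF guidance. No new data are collected and the sample size does not change. The Sponsor can re-derive the microbiological ratings from the culture data. Clinical ratings already entered for affected subjects would need a blinded query to the investigator.

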4.2.3.2 Safety Endpoints

In support of the primary objective to evaluate the safety and tolerability profile of IMI/REL, the safety and tolerability of IMI/REL (as well as the safety of the comparator, CMS + IMI) will be assessed by clinical evaluation of adverse experiences and inspection of other study parameters including vital signs, physical examinations, and standard laboratory safety tests at time points specified in the Trial Flow Chart. Adverse experiences are graded and recorded according to Section 7.2. Subjects may be asked to return for unscheduled visits in order to perform additional safety monitoring.

In addition, due to concern for potential renal toxicity of colistin, the relative rates of nephrotoxicity of IMI/REL and CMS + IMI will be evaluated as a secondary endpoint in this study. Evaluation of potential nephrotoxicity will be performed based on laboratory test results from blood samples.

As discussed in Section 4.1.3, the reported incidence of nephrotoxicity associated with colistin administration is variable. In addition to the lack of a standard dosing algorithm for colistin, a major difficulty in determining the true incidence of nephrotoxicity associated with intravenous colistin therapy is the absence of a standardized and consistently applied definition of nephrotoxicity. In this study, the definition of nephrotoxicity will be based on alterations in baseline serum creatinine and renal function as described in Table 9. Serum creatinine level as well as creatinine clearance are commonly used in clinical practice to measure renal function. In addition, there is evidence that changes in serum creatinine are associated with an increase in short-term morbidity and even mortality, thus making serum creatinine an appropriate marker for measuring acute kidney injury [73]. Changes in

creatinine and renal function have frequently been used in the literature to describe colistin-associated nephrotoxicity [13, 17, 21-23, 26, 74, 75, 76].

Table 9 Criteria for Defining Nephrotoxicity

Baseline Renal Function Category	Baseline Serum Creatinine Level	Definition of Nephrotoxicity
Normal	<1.2 mg/dL	Doubling of serum creatinine (to >1.2 mg/dL), OR Reduction in the calculated creatinine clearance ^a (CL _{Cr}) of ≥50%.
Pre-Existing Renal Dysfunction	≥1.2 mg/dL	Increase in serum creatinine by ≥1 mg/dL, OR Reduction from baseline in calculated CL _{Cr} ^a of ≥20%, OR Need for RRT.
RRT= Renal replacement therapy ^a Calculated from serum creatinine using the equation provided in Section 5.2.1.1.		

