- porphyria
- cystic fibrosis
- granulomatous disease

10. is anticipated to be treated with any of the following medications during the course of study therapy:

- valproic acid or divalproex sodium (or has used valproic acid or divalproex sodium in the 2 weeks prior to screening)
- concomitant IV, oral, or inhaled antimicrobial agents with known coverage of Gram-negative bacteria of interest (i.e., Enterobacteriaceae, *Pseudomonas* spp. and Gram-negative anaerobic bacilli), in addition to those designated in the study treatment groups.

NOTE: Use of IV vancomycin, IV daptomycin, or IV linezolid to treat confirmed or suspected methicillin-resistant *S. aureus* (MRSA) infection, use of IV linezolid or IV daptomycin to treat confirmed or suspected vancomycin-resistant *Enterococcus* spp. (VRE) infection, or use of trimethoprim-sulfamethoxazole (TMP/SMX) or other standard-of-care agent for prophylaxis of opportunistic infection (e.g., *Pneumocystis jiroveci* infection) in immunocompromised subjects is allowed. Daptomycin is not indicated for the treatment of HABP/VABP (Refer to Section 5.5).

11. has an estimated or actual creatinine clearance of less than 15 mL/min at screening based on the findings of local laboratory values. Creatinine clearance in mL/min may be calculated from serum creatinine concentration by the Cockcroft-Gault (C-G) equation:

$$\text{Creatinine clearance (Males)} = \frac{(\text{weight in kg}) \times (140 \text{ minus age})}{(72) \times (\text{creatinine in mg/dL})}$$

Creatinine clearance (Females) = 0.85 X the value obtained using the formula above

12. is currently undergoing hemodialysis or peritoneal dialysis.
13. has a history or current evidence of any condition, therapy, laboratory abnormality, or other circumstance that, in the opinion of the investigator, might confound the results of the study, interfere with the subject's participation for the full duration of the study, or pose additional risk in administering the study drugs to the subject.
14. is currently participating in, or has participated in, any other clinical study involving the administration of investigational or experimental medication (not licensed by regulatory agencies) at the time of the presentation or during the previous 30 days prior to screening or is anticipated to participate in such a clinical study during the course of this trial.

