5.2.1 Dose Selection/Modification

5.2.1.1 Dose Selection

For subjects with renal insufficiency, the dose of IMI/REL (in Treatment Group 1 or Treatment Group 3) and IMI (in Treatment Group 2) must be adjusted based upon the degree of renal function impairment, as determined by the estimated or actual creatinine clearance. It is important to note that if a change in the subject's creatinine clearance during IV study therapy could result in dosage adjustments at any time during IV therapy. Dose adjustments according to creatinine clearance are included in [Table 11](#).

Creatinine clearance in mL/min may be calculated from serum creatinine concentration by the C-G equation:

$$\text{Creatinine clearance (Males)} = \frac{(\text{weight in kg}) \times (140 - \text{minus age})}{(72) \times (\text{creatinine in mg/dL})}$$

$$\text{Creatinine clearance (Females)} = 0.85 \times \text{the value obtained using the formula above}$$

Subjects in Treatment Group 2 will also receive colistin as CMS. Upon randomization and initiation of IV study therapy, the dosage of the first dose of CMS for Treatment Group 2 subjects will depend on the subject's previous history of receipt of colistin within the 72 hours prior to entry in the study. Specifically, if a loading dose >200mg CBA (corresponding to ~ 470 mg CMS or 5.9 million IU) was administered prior to entry, the subject should begin maintenance doses described in [Table 12](#) upon initiation of IV study therapy. It should be noted that a loading dose is defined based on the dosage of any individual dose(s) administered rather than the total dosage over a series of doses in a subject who has received >1 dose prior to entry. If the subject has not received a loading dose (i.e., an individual dose \geq 200 mg CBA) prior to study entry, the protocol-specified loading dose of CMS of 300 mg CBA (corresponding to ~ 720 mg CMS or ~9 million IU) should be provided as shown in [Table 12](#), regardless of the dosage previously administered.

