- ^d The details of any primary or secondary infection-site diagnoses (HABP/VABP, cIAI and/or cUTI) will be documented separately on the appropriate eCRF(s). Details should include the diagnosis and an additional diagnostic details associated with the infection site (e.g., characterization of the complicated nature of the cIAI and/or cUTI).
- ^e For the purpose of monitoring renal function during IV treatment, the most recently collected creatinine clearance should also be reported to IVRS daily to support dosage determination. (refer to Table 11 and Table 12 in Section 5.2.1.1). Any local or central laboratory abnormalities in serum creatinine that result in an adverse event or a dose adjustment.
- ^f Vital signs should be performed and documented on the appropriate electronic case report forms (eCRFs) at the randomization visit (Day 1) prior to administration of the first dose of study therapy and daily during IV study therapy. Vital signs should also be performed and documented at the additional visits specified.
- ^g Enter weight if a clinically significant weight change occurred and resulted in a change in CrCl category.
- ^h Monitor for adverse events and local infusion tolerability and collect infection-specific clinical signs and symptoms daily during IV study therapy and adverse experiences for 14 days after completion of IV study therapy. Laboratory abnormalities that emerge during IV therapy and are considered adverse experiences by the investigator must be followed until resolved or stabilized. Serious adverse experiences that are considered by the investigator to be possibly, probably or definitely related to the investigational product that is brought to the attention of the investigator at any time outside of 14 days post-therapy also must be reported immediately to the Sponsor.
- ⁱ Clinical signs and symptoms, radiographic (daily reporting not required for radiographic findings) and laboratory characteristics associated with the primary bacterial infection and any secondary bacterial infection sites (see Table 13) will be reviewed and documented on the appropriate electronic case report forms (eCRFs) daily during IV study therapy and at the additional visits specified.

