8.2.4.2 Safety Analysis Populations

The ASaT population will be used for the analysis of safety data in this study. The ASaT population consists of all subjects who received at least one dose of IV study therapy. The ASaT includes non-randomized subjects in Treatment Group 3 (IMI/REL), as well as randomized subjects in Treatment Group 1 (IMI/REL) and Treatment Group 2 (CMS + IMI). Subjects will be included in the therapy group corresponding to the study therapy they actually received for the analysis of safety data using the ASaT population. Subjects who are administered incorrect study therapy for the entire treatment period will be included in the therapy group corresponding to the study therapy actually received.

At least one laboratory or vital sign measurement obtained subsequent to at least one dose of IV study therapy is required for inclusion in the analysis of each specific parameter. To assess change from baseline, a baseline measurement is also required.

Since the assessment of treatment-emergent nephrotoxicity requires serum creatinine measurements at baseline and after at least one dose of IV study therapy, subjects who have missing data at either of these time points will be excluded from the summaries/analyses of this endpoint.

Details on the approach to handling missing data for safety analyses are provided in Section 8.2.5 (Statistical Methods).

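### Table 9's nephrotoxicity definition is internally inconsistent: its clearance limbs make two creatinine thresholds inoperative, and need for RRT counts in only one baseline category

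*Combined protocol and SAP*

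**What the plan says.** Treatment-emergent nephrotoxicity is a key secondary objective (Section 3.2.1) and a Tier 1 safety event (Section 8.2.3.2). It is the only primary or key secondary endpoint in Table 16 with a between-group test, a two-sided Fisher exact test in the ASaT population.

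Table 9 in Section 4.2.3.2 sets the definition by baseline serum creatinine:

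- Below 1.2 mg/dL (Normal): "Doubling of serum creatinine (to >1.2 mg/dL), OR Reduction in the calculated creatinine clearance" of at least 50%.
- At or above 1.2 mg/dL (Pre-Existing Renal Dysfunction): "Increase in serum creatinine by ≥1 mg/dL, OR Reduction from baseline in calculated CL" of at least 20%, or need for RRT.

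The footnote on clearance reads "Calculated from serum creatinine using the equation provided in Section 5.2.1.1". Section 5.2.1.1 says "Creatinine clearance in mL/min may be calculated from serum creatinine concentration by the C-G equation": weight times (140 minus age), divided by 72 times creatinine, with a factor of 0.85 for women. On weight, the Section 6.0 flow chart says "Enter weight if a clinically significant weight change occurred and resulted in a change in CrCl category".

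Section 8.2.4.2 requires a creatinine at baseline and after at least one dose, and states that "subjects who have missing data at either of these time points will be excluded from the summaries/analyses of this endpoint".

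**The concern.** Each row of Table 9 offers a creatinine criterion and a clearance criterion joined by OR, as if they measured different things. The clearance is a function of the same creatinine value, so the looser of the two decides and the other has no effect. Two printed thresholds, the 1.2 mg/dL floor and the 1 mg/dL rise, therefore do not do what a reader would take them to do. The two rows also differ sharply in sensitivity on either side of 1.2 mg/dL.

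Separately, RRT is absent from the Normal row. Under the literal wording, a subject with a normal baseline who is dialysed is an event only if a recorded creatinine has doubled. In the other row, a subject dialysed before any post-dose creatinine meets Table 9 but is removed by Section 8.2.4.2. In either case the most severe renal outcome can go uncounted in the one key endpoint that is tested between arms.

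**Working it through.** **The plan's own figure.** Section 8.2.7 says a difference of about 3 events favouring IMI/REL gives p<0.05. Two-sided Fisher exact p-values, IMI/REL events v CMS + IMI events:

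| Events | N=30 v 15 (Table 19) | N=36 v 18 (planned randomized numbers) |
|---|---|---|
| 0 v 3 | 0.032 | 0.033 |
| 1 v 4 | 0.036 | 0.038 |
| 2 v 5 | 0.032 | 0.034 |
| 3 v 6 | 0.042 | 0.047 |
| 0 v 2 | 0.106 | 0.107 |
| 1 v 3 | 0.101 | 0.103 |

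The statement reproduces at both sizes. One event fewer in the comparator arm moves 0 v 3 or 1 v 4 from below 0.05 to above 0.10. (Three Table 19 cells do not reproduce: 1 v 2 is 0.254, 3 v 3 is 0.384 and 2 v 4 is 0.158. None crosses 0.05.)

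**Clearance in terms of creatinine.** Inputs are the Table 9 limbs and the Section 5.2.1.1 equation. With age and weight fixed, clearance is proportional to 1/SCr, so

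fractional fall = 1 − SCr0/SCr1.

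- Fall of at least 50%: SCr1 ≥ 2.00 × SCr0.
- Fall of at least 20%: SCr1 ≥ 1.25 × SCr0.

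**Normal row.** The clearance limb is the doubling without the floor. The floor would matter only where doubling does not exceed 1.2, that is for baselines up to 0.60 mg/dL, and there the clearance limb is met anyway: 0.4 to 0.8 and 0.5 to 1.0 mg/dL are both events. A search over baselines in steps of 0.01 mg/dL found no Normal-row case that met the creatinine limb but not the clearance limb.

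**Pre-existing row.** The clearance limb needs a rise of 0.25 × SCr0. This reaches 1 mg/dL only when SCr0 = 1/0.25 = 4.0 mg/dL.

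| Baseline SCr (mg/dL) | Creatinine limb met at | Clearance limb met at | Rise that decides |
|---|---|---|---|
| 1.19 (Normal) | 2.38 | 2.38 | +1.19 (100%) |
| 1.20 | 2.20 | 1.50 | +0.30 (25%) |
| 2.0 | 3.00 | 2.50 | +0.50 (25%) |
| 3.0 | 4.00 | 3.75 | +0.75 (25%) |
| 4.0 | 5.00 | 5.00 | +1.00 (tie) |
| 5.0 | 6.00 | 6.25 | +1.00 (20%) |

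The 1 mg/dL limb decides only above 4.0 mg/dL. Section 5.1.3.1 excludes a subject who "has an estimated or actual creatinine clearance of less than 15 mL/min at screening". For an illustrative 70 kg man aged 60, a clearance of 15 corresponds to a creatinine of 70 × 80/(72 × 15) = 5.19 mg/dL, so baselines above 4.0 are admissible but uncommon territory.

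**Step at 1.2 mg/dL.** With the creatinine limbs alone, the value needed would go from 2.38 to 2.20 mg/dL across the boundary. With the clearance limbs it goes from 2.38 to 1.50. For the same illustrative man these baselines are clearances of 65.4 and 64.8 mL/min.

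**Dependence on weight.** The plan does not say which weight enters the endpoint. If a re-recorded weight were used, a 10% gain with an exact doubling would give a fall of 1 − 1.10/2 = 45%, and the two limbs would separate.

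**RRT.** Set side by side: Table 9 gives RRT as a sufficient criterion in one row, with no creatinine needed; the other row has no such criterion; Section 8.2.4.2 makes a post-dose creatinine a condition for being analysed at all. These cannot all be applied as written.

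**The case against.** Several points on the other side stand. A redundant limb in an OR rule does not by itself misclassify anyone, any baseline-dependent definition has a step somewhere, and Section 4.2.3.2 openly says that no standard definition exists. The step at 1.2 mg/dL is therefore partly a design choice.

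The RRT gap should touch few subjects. Chemistry is drawn on Day 3, every 3 days to EOT, and at EFU and Day 28, so most subjects will have a post-dose creatinine, and most normal-baseline subjects who need RRT would have doubled it. Dialysis is also a reason to stop study therapy under Section 5.8, so it does not vanish from the record.

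A reader might go further and infer that chance imbalance in baseline renal category, which is not a stratification factor, invalidates the Fisher comparison. The documents do not support that. Assume event risks of 40% (pre-existing) and 10% (normal), no drug effect, and 36 v 18 subjects. An imbalance of 20 points or more in either direction then has probability 11.5%, 14.1% and 14.9% at prevalences of 30%, 40% and 50%; towards the comparator it is 6.0% to 7.5%. It would shift the arm difference by 0.20 × (40 − 10) = 6 points, about one event in 18. The two-sided false-positive rate is nevertheless about 3.5% overall, and 4.5% to 5.4% given an imbalance of about 20 points. Randomization already covers this, and replacing the test with an exact Mantel-Haenszel analysis would be a preference, not a correction.

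What the objection does not answer is the wording: the floor conflicts with its own row, the rows treat RRT differently, and Section 8.2.4.2 contradicts the RRT criterion.

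**Conclusion.** The concern holds as an internal inconsistency in the endpoint definition. At constant weight, the 1.2 mg/dL floor excludes no one, the 1 mg/dL limb is never met first below a baseline of 4.0 mg/dL, and the rise needed falls from 1.19 to 0.30 mg/dL between baselines of 1.19 and 1.20. Followed literally, Table 9 and Section 8.2.4.2 can score a dialysed subject as a non-event or drop that subject from the analysis.

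The number affected is probably small, and the documents give no basis for a frequency. Type I error is not inflated. The point still warrants a change because the tested comparison turns on about three events, so one subject classified differently can move the p-value from 0.032 to 0.106. The algebra rests on one weight being used at both times; the 40% and 10% risks above are assumptions used only to test the stronger reading.

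**What to change.** Before unblinding, amend Table 9 and Sections 8.2.4.2 and 8.2.5.2:

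1. Reconcile the two rows with Section 8.2.4.2 so that RRT counts as a nephrotoxicity event in both baseline categories, with or without a post-dose creatinine. Confirm that the eCRF captures any RRT, including after IV therapy ends: the Section 5.8 trigger names only hemodialysis and peritoneal dialysis, and only as reasons to stop therapy.
2. Reconcile the Normal-row floor with its clearance limb, either by applying it to both limbs or by deleting it. State which weight is used to calculate clearance for the endpoint.
3. Keep the Fisher test. Report nephrotoxicity by baseline renal category and add one supportive analysis applying a single relative rule (creatinine doubling or RRT) to all subjects.

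Item 3 leaves the step at 1.2 mg/dL in the main definition but makes its influence visible. The cost is a short amendment, an eCRF check, a few extra tables and possibly a slightly different event count. Creatinine sampling does not change.
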